9.1 Discontinuation and completion

9.1.1 Study treatment discontinuation and study discontinuation

Discontinuation of study treatment for a participant occurs when study treatment is stopped earlier than the protocol planned duration and can be initiated by either the participant or the investigator.

The investigator must discontinue study treatment for a given participant if, he/she believes that continuation would negatively impact the participant's well-being.

Study treatment must be discontinued under the following circumstances:

- Participant/guardian decision
- Any situation in which study participation might result in a safety risk to the participant

If a female becomes pregnant during the study, it is recommended to discontinue treatment with LNP023. However, after an individual benefit-risk assessment by the investigator, LNP023 continuation may be considered in exceptional circumstances. Counseling should be provided to the participant on the appropriate treatment for PNH during pregnancy. The outcome of the discussion with the participant, reflecting benefit-risk considerations, should be documented in the participant's file.

If treatment with iptacopan has to be discontinued immediately, i.e. because of a significant safety risk, appropriate replacement therapy must be offered to participants based on investigator's judgment and local availability (including starting anti-C5 antibody treatment if available).

Close monitoring of participants for signs and symptoms of hemolysis should be performed upon iptacopan discontinuation. It is recommended to monitor at minimum for: increase in LDH, decrease in hemoglobin level [REDACTED] increase in serum creatinine, thrombosis, and change in mental status. If serious hemolysis occurs, the Investigator should consider the following supportive treatments (and record them in the appropriate CRF pages):

- Blood transfusion (packed RBCs)
- Exchange transfusion if the PNH RBCs are >50% of the total RBCs by flow cytometry
- Corticosteroids
- Anticoagulation
- Any other supportive treatment or therapy as judged by the investigator

A visit one week after permanent discontinuation of iptacopan should occur for the following assessments: LDH, creatinine, hemoglobin, coagulation/thrombosis markers (Prothrombin time

(PT)/INR, activated partial thromboplastin time (aPTT), D-dimer, and fibrinogen), [REDACTED] dipstick urinalysis, [REDACTED] and all adverse events. All data collected will be entered in the appropriate CRF page.

If treatment with iptacopan is discontinued prematurely but it is not warranted to immediately discontinue iptacopan treatment, e.g., discontinuation due to participant/guardian decision, it is recommended to consider appropriate replacement therapy based on investigator's judgment and local availability (including starting anti-C5 antibody treatment if available). In addition, it should be considered to taper down iptacopan over a period of 14 days, as follows:

- 3 capsules of 10 mg iptacopan taken in the evening (once daily) for 7 days
- 1 capsule of 10 mg iptacopan taken in the evening (once daily) for 7 days

The investigator should consider the proposed monitoring and supportive treatments listed above in case serious hemolysis occurs. For iptacopan tapering, weekly visits are recommended until one week after last iptacopan dose for the following assessments: LDH, creatinine, hemoglobin, coagulation/thrombosis markers (PT/INR, aPTT, D-dimer, and fibrinogen), [REDACTED] dipstick urinalysis, [REDACTED] and all adverse events. All data collected will be entered in the appropriate CRF page.

If discontinuation of study treatment occurs, the investigator should make a reasonable effort to understand the primary reason for the participant's premature discontinuation of study treatment and record this information.

Participants who discontinue study treatment or who decide they do not wish to participate in the study further should NOT be considered withdrawn from the study UNLESS they withdraw their consent (see 'Withdrawal of Informed Consent' [Section 9.1.2](#)).

Where possible, they should return for the assessments indicated in the Assessment Schedule. If they fail to return for these assessments for unknown reasons, every effort (e.g. telephone, e-mail, letter) should be made to contact the participant/pre-designated contact as specified in the lost to follow-up section. This contact should preferably be done according to the study visit schedule.

Participants who permanently discontinue study medication during the Core treatment period, should complete the visits as scheduled up to Week 24.

Participants who permanently discontinue study medication during the Extension treatment period, and if possible, should complete the visits as scheduled up to Week 48.

If the participant cannot or is unwilling to attend any visit(s), the site staff should maintain regular telephone contact with the participant, or with a person pre-designated by the participant. This telephone contact should preferably be done according to the study visit schedule.

After study treatment discontinuation, at a minimum, in abbreviated visits, the following data should be collected at clinic visits or via telephone/email contact:

- New / concomitant treatments
- Safety laboratory assessments
- Adverse Events / Serious Adverse Events

All dose changes must be recorded on the appropriate CRF. The investigator must also contact the IRT to register the participant's discontinuation from study treatment.

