6.2.2 Prohibited medication

Use of the treatments listed below are not allowed during iptacopan administration.

- Any other complement inhibitors, including anti-C5 antibody, are prohibited for the entire study treatment. If anti-C5 antibody is started, the patient should permanently discontinue iptacopan.
- Live vaccines are prohibited for the entire study treatment duration.
- Preclinical studies have shown that systemic disposition of iptacopan is primarily mediated by metabolic clearance, predominantly by CYP2C8 and to a smaller extent by direct glucuronidation. In addition, some contribution from direct renal (approximately 20%) and

direct biliary excretion (around 5 to 10%) is anticipated. iptacopan is also a substrate for the organic anion-transporting polypeptide (OATP) hepatic uptake transporter (see above). To ensure participant safety, co-medications that inhibit multiple disposition mechanisms of iptacopan (e.g. Gemfibrozil) are prohibited. The same applies to strong CYP2C8 inhibitors (main clearance pathway) such as clopidogrel.

- Gemfibrozil (a potent inhibitor of metabolizing enzymes CYP2C8, UGT1A and liver uptake transporter OATP1B1) must be interrupted at least 48 hours before first iptacopan dose until end of iptacopan treatment (and replaced with another appropriate medication used for that indication).
- Strong inhibitors of CYP2C8 such as clopidogrel must be interrupted 7 days before first iptacopan dose until end of iptacopan treatment (and replaced with another appropriate medication).
- Medications that are either “sensitive substrates” for the efflux transporter P-gp or have a narrow therapeutic index (NTI) and are substrates for P-gp should not be administered with iptacopan (interrupted 48 hours before first iptacopan dose). Typical examples are digoxin, quinidine, paclitaxel, fentanyl and phenytoin. However, if no alternative treatment is available, a staggered dosing approach is recommended (refer to [Section 6.2.1.1](#)). The anti-coagulation drug dabigatran which is also a P-gp substrate should not be used in combination with iptacopan and a staggered dosing is also not recommended.

Concomitant medication listed under exclusion criterion 16 is prohibited if not on a stable regimen prior to Screening, for the time periods indicated.

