The duration of exposure to study treatment will be computed and summarized as the duration of treatment, but excluding temporary treatment interruptions. To establish the start of an interruption, the same rules should apply as for end of the duration of treatment described above.

An interruption will be defined as at least one full day without any dose.

Cumulative duration exposure on iptacopan 200 mg b.i.d based on SAF will be summarized as a categorical variable classified into ≤ 4 , ≤ 8 , ≤ 12 , ≤ 16 , ≤ 20 , ≤ 24 , ≤ 28 , ≤ 32 , ≤ 36 , ≤ 40 , ≤ 44 , ≤ 48 weeks.

The duration of exposure will be the basis for the computation of the dose intensity and the relative dose intensity. The dose intensity for patients on iptacopan 200 mg bid will be computed as the ratio of actual cumulative dose received and actual duration of exposure. Relative dose intensity for patients on iptacopan 200 mg b.i.d will be computed as the ratio of dose intensity

and planned dose intensity. The planned dose intensity for patients on iptacopan 200 mg bid will be 400 mg/day. The dose intensity for patients on iptacopan will be summarized as a categorical variable classified into the categories stated in [Table 2-1](#). Relative dose intensity will also be summarized on a continuous scale as well as considering categories (%): ≤ 75 , > 75 , > 90 -100 and summaries on dose intensities will be presented on SAF.

The information on iptacopan +transfusions will be summarized as a categorical variable considering the dose intensity and transfusions in the core treatment period. Summaries on the categories stated in [Table 2-1](#). Such summaries will be presented on SAF.

For participants on iptacopan, the calculation of duration of treatment, exposure, dose intensity and relative dose intensity will include the investigational treatment iptacopan 200 mg b.i.d as well as the iptacopan tapering doses (if applicable).

Table 2-1 Summary on dose intensity and transfusions for patients on iptacopan

Dose intensity	Dose intensity and transfusions
<400 mg/day	<400 mg/day + no transfusion
400 mg/day	<400 mg/day + 1 transfusion
	<400 mg/day + ≥ 2 transfusions
	400 mg/day + no transfusion
	400 mg/day + 1 transfusion
	400 mg/day + ≥ 2 transfusions

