2.4.2 Prior, concomitant and post therapies

Medications and significant non-drug therapies started and stopped prior to study treatment, and those taken concomitantly, will be summarized based on SAF. Among the concomitant medications, rescue medications will be summarized based on SAF. The medications and significant non-drug therapies will be classified into “prior”, “concomitant”, “post-treatment” based on the start/end dates. The rescue therapy will be used for analysis as it is reported by the investigator under the subcategory of Rescue Medications/Therapy on the Concomitant Medication, Surgical and Medical Procedures CRF pages. Prior: Any medication and significant non-drug therapy with a start date and end date before Day 1.

Concomitant: Any medication or significant non-drug therapy administered at least once during the duration of the treatment (as defined in [Section 2.4.1](#)). It does not include 7 days after the last dose of iptacopan as in the definition of the on-treatment period for treatment emergent adverse event (TEAE). Medications started prior to first day of study drug intake and continuing after study drug start will be counted as concomitant.

Post-treatment medications will be defined as any medication with start date after the end of treatment (any dose).

A therapy started within 7 days after the last dose of iptacopan is not considered as concomitant although some TEAEs leading to concomitant medications may be reported in that period. The objective of this convention is to avoid reporting as concomitant medication some post treatment therapies targeting the study indication.

Prior, concomitant, post-treatment medications will be summarized according to the Anatomical Therapeutic Chemical (ATC) classification system. More than one ATC class per medication is possible and the medication will be reported under all applicable classes.

Prior, concomitant, post-treatment therapies will be recorded and summarized separately for surgical and medical procedures.

All vaccinations received by patients any time during the study (including core treatment period, extension treatment period) will be tabulated by serogroup/polyvalent and for each period. All vaccinations will also be recorded as prior and/or concomitant medication, as appropriate.

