2.7 Safety analyses

Unless otherwise specified all safety summaries will be presented by SAF. Safety summaries based on only core treatment period and overall (based on information from core treatment period and extension treatment period) will be produced as appropriate.

Safety summaries (tables, figures) include only data from the on-treatment period with the exception of baseline data which will also be summarized where appropriate (e.g., change from baseline summaries). In particular, summary tables for adverse events (AEs) will summarize only on-treatment events, with a start date during the on-treatment period (treatment-emergent AEs). In addition, a separate summary of death events including on treatment and post treatment deaths will be provided if appropriate.

The on-treatment period lasts from the date of first administration of study treatment to 7 days after the date of the last actual administration (including core treatment period, extension treatment period and tapering procedures after permanent treatment discontinuation) of iptacopan which covers slightly more than 5 times the estimated half-life of iptacopan.

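### Protocol 9.1.1 suggests anti-C5 and an iptacopan taper together without a sequence, while 6.2.2 bars anti-C5 during iptacopan dosing

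*Protocol*

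**What the plan says.** Protocol 6.2.2 opens its list of prohibited medication with "Use of the treatments listed below are not allowed during iptacopan administration". The first entry reads "Any other complement inhibitors, including anti-C5 antibody, are prohibited for the entire study treatment", followed by "If anti-C5 antibody is started, the patient should permanently discontinue iptacopan".

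Protocol 9.1.1 separates two kinds of early stop. For an immediate stop on safety grounds no taper is described, so this point does not arise. For a stop that is not urgent, "it is recommended to consider appropriate replacement therapy", and starting anti-C5 is named as an option where it is available. The next sentence begins "In addition, it should be considered to taper down iptacopan over a period of 14 days" and gives two seven-day steps using 10 mg capsules. Protocol Table 6-1 lists those capsules as investigational drug, used only for tapering.

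In SAP 2.4.1 the calculation of treatment duration, exposure and dose intensity "will include the investigational treatment iptacopan 200 mg b.i.d as well as the iptacopan tapering doses (if applicable"). SAP 2.7 runs the on-treatment period to 7 days after the last actual administration, "including core treatment period, extension treatment period and tapering procedures after permanent treatment discontinuation".

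**The concern.** The two protocol sections address the same patient on the same days. Section 9.1.1 places anti-C5 and the taper side by side, and its linking phrase reads most naturally as doing both. Section 6.2.2 does not allow the combination while any iptacopan is given. Section 9.1.1 contains no exception to 6.2.2, no cross-reference to it and no timing.

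The timing matters because Protocol 4.5 names hemolysis after stopping a complement inhibitor as a risk specific to PNH and relies on 9.1.1 to manage it. Sites could handle the same discontinuation differently, and some could commit a protocol deviation by following the discontinuation section.

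There is also a reporting consequence. Because the taper and the following 7 days are on-treatment, adverse events that start after anti-C5 has begun enter the treatment-emergent tables. Nothing in those tables shows that a second complement inhibitor was present.

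**Working it through.** **Does the taper fall under 6.2.2?** The opening sentence of 6.2.2 covers any iptacopan administration, not only 200 mg b.i.d. The taper capsules are iptacopan and are investigational drug. The protocol glossary defines study treatment discontinuation as permanently stopping study drug, which has not happened while taper capsules are being taken. On the wording, taper days are days of iptacopan administration.

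**Which courses of action breach 6.2.2?**
- Anti-C5 and taper at the same time: invited by 9.1.1, not allowed by 6.2.2.
- Taper first, anti-C5 after the last taper dose: consistent with both.
- Anti-C5 without a taper, or a taper without anti-C5: consistent with both, since each step in 9.1.1 is only to be considered.

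**Day count.** Inputs: taper steps of 7 and 7 days (Protocol 9.1.1); on-treatment tail of 7 days (SAP 2.7). The plan's own taper length is reproduced: 7 + 7 = 14 days.

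Assumptions: the last 200 mg dose is day 0, the taper fills days 1 to 14, and every day from the first anti-C5 dose onward counts as an anti-C5 day. The on-treatment window then ends on day 14 + 7 = 21. After a stop without a taper it ends on day 7.

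Let s be the day anti-C5 starts. The documents do not give it, so a range is shown.
- Concurrent dosing days = 14 − s + 1 = 15 − s, for s from 1 to 14, and 0 from day 15.
- Anti-C5 days inside the on-treatment window = 21 − s + 1 = 22 − s.

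| Anti-C5 start | Concurrent dosing | Anti-C5 days in window |
|---|---|---|
| day 1 | 15 − 1 = 14 | 22 − 1 = 21 |
| day 8 | 15 − 8 = 7 | 22 − 8 = 14 |
| day 15 | 0 | 22 − 15 = 7 |

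**Do the planned displays separate these events?** SAP 2.7.1 and Protocol 12.5.2 plan a separate adverse event summary for tapering. SAP 2.7.1 also reports separately treatment-emergent SAEs and events in the PNH haemolysis and thrombosis AESI that occur after 200 mg b.i.d. stops. SAP 2.7.1.1 repeats this for that AESI, with a listing. All of these split events by iptacopan dose. None splits them by anti-C5 start, and a non-serious infection would not appear in the AESI display.

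**The case against.** The strongest reply is that the sections can be read together. Section 6.2.2 says that starting anti-C5 should lead to permanent discontinuation of iptacopan, and 9.1.1 is the procedure for permanent discontinuation. SAP 2.7 even places tapering after permanent discontinuation. On that view the taper is part of stopping. This reading is available, but the texts do not settle on it. The opening sentence of 6.2.2 covers any administration, the glossary ties discontinuation to stopping the drug, and SAP 2.7.1 places tapering before complete discontinuation.

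A reader might infer that a site cannot comply with both sections, or that 9.1.1 instructs sites to start anti-C5. The documents do not support either. Both steps are for consideration, and sequencing or omitting one satisfies both sections. Nor do they show that some participants would be left with neither drug: a site that delays anti-C5 still has the taper, and a site that forgoes the taper can start anti-C5.

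A reader might also infer that events in the overlap are simply reported as iptacopan events. That overlooks the separate displays listed above. Calling taper-period events treatment-emergent is not an error, because the participant is still taking iptacopan. With about 40 participants and all adverse events listed, what remains is small: no display identifies events that follow the first anti-C5 dose.

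Finally, a reader might think that SAP 2.4.2 defeats its own aim, "The objective of this convention is to avoid reporting as concomitant medication some post treatment therapies targeting the study indication", by treating anti-C5 started during a taper as concomitant. That convention concerns therapies started within 7 days after the last dose. A drug taken while iptacopan is still being dosed is properly concomitant, and relabelling it post-treatment would hide the overlap.

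**Conclusion.** The point holds as an unreconciled conflict between 6.2.2 and 9.1.1 when the two steps are taken together, caused by missing timing and a missing cross-reference. It deserves correction because it sits in the procedure that Protocol 4.5 relies on for hemolysis after stopping.

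The size is 0 to 14 days of concurrent dosing, and 7 to 21 anti-C5 days inside the on-treatment window, for anti-C5 starts from day 15 back to day 1. A start after day 15 gives fewer than 7 such days. These figures assume that the taper begins the day after the last 200 mg dose and is completed.

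The number of participants cannot be derived from the documents and may be small. It covers non-urgent discontinuers with access to anti-C5, and possibly those who decline the extension or the roll-over program and are directed to 9.1.1. Protocol 4.1 describes the trial as supporting registration where anti-C5 is not available, which limits the reach.

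The primary responder analysis and its 15% threshold do not depend on this point.

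**What to change.** Amend Protocol 6.2.2 and 9.1.1 so that both state the same rule on whether anti-C5 and taper-dose iptacopan may overlap, and cross-refer each to the other. Which rule applies is a clinical decision for the sponsor, and none is proposed here.

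In SAP 2.7.1, flag treatment-emergent adverse events with onset on or after the first anti-C5 dose. Protocol 9.1.1 already lists new and concomitant treatments among the minimum data to collect after discontinuation, so no new data collection is needed. Leave the SAP 2.4.2 classification as it is.

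The cost is a short protocol edit, one SAP sentence and one extra flag in the adverse event outputs.
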